HADS was developed for use in medically ill patients and validated in palliative care populations.^{44,45} It is a self-report questionnaire consisting of 14 items, and subjects rate how they felt during the previous week on a 4-point Likert scale. The HADS consists of an anxiety and depression subscale (0–21 points each), and total scores can range from 0 to 42. Higher scores indicate more severe depression and anxiety. Participating subject's caregivers also will complete the HADS at V1, V5 and V6a,b...

Estimated time for administration: 5 minutes

Functional Assessment of Chronic Illness Therapy - Palliative Care 14 (Baseline [V1], V5, V6a,b...)

FACIT-Pal 14 measures quality of life in palliative care patients. It has good internal consistency and there is evidence of construct validity.⁴⁶ FACIT-Pal 14 consists in 14 items, and subjects rate how they felt during the previous week on a 5-point Likert scale.

Version Date: April 18, 2023 Confidential

Estimated time for administration: 3 minutes

PROMIS® Pain Interference Scale – 8 items (Baseline [V1], V5, V6a,b...)

The PROMIS is a National Institutes of Health (NIH) Roadmap initiative that aims at providing precise, reliable, valid, and standardized questionnaires measuring patient-reported outcomes across the domains of physical, mental, and social health.⁵¹

The PIS measures the self-reported consequences of pain on relevant aspects of a person's life and may include the extent to which pain hinders engagement with social, cognitive, emotional, physical, and recreational activities.⁵² We will use 8 validated items pertaining to social and emotional consequences of pain during the previous week, that subjects will rate on a 5-point Likert scale. The PIS will only be collected from a patient if the patient indicates pain at a given assessment period.

Estimated time for administration: 2 minutes

Life Attitude Profile – revised, Death acceptance subscale (Baseline [V1], V6a)

LAP-R Death Acceptance is a validated, self-rated 9-item, 7-point Likert scale assessing acceptance and anxiety about death.⁵³

Estimated time for administration: 2 minutes

Social Isolation Scale-6a (Baseline [V1], V5, V6a,b...)

The PROMIS® SIS-6a assesses perceptions of being avoided, excluded, detached, disconnected from, or unknown by, others. We will use the short form of the instrument consisting in a 6-item, 5-point Likert scale.⁵⁴

Estimated time for administration: 2 minutes

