13.2.2. Efficacy outcomes

Global quality of life: FACIT-Pal 14

Physical domain: PIS

• Psychological domain: HADS A and D; LAP-R; CEQ

• Social domain: SIS

• Spiritual domain: FACIT-sp; DS- II; SAHD; MEQ-30

• Caregiver quality of life and psychological distress: CarGOQoL; HADS A and D

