	3	Not at all	3		Very seldom

Please check you have answered all the questions

Scoring:	
Total score: Depression (D)	Anxiety (A)
0-7 = Normal	
8-10 = Borderline abnormal (borderline case	e)
11-21 = Abnormal (case)	•

A6 – Functional Assessment of Chronic Illness Therapy - Palliative Care 14

Below is a list of statements that other people with your illness have said are important. Please circle or mark one number per line to indicate your response as it applies to the past 7 days.

		Not at all	A little bit	Some- what	Quite a bit	Very much
GP1	I have a lack of energy	0	1	2	3	4
GP2	I have nausea	. 0	1	2	3	4
GP4	I have pain	. 0	1	2	3	4
GE6	I worry that my condition will get worse	0	1	2	3	4
GF3	I am able to enjoy life	0	1	2	3	4
GF5	I am sleeping well	0	1	2	3	4
GF7	I am content with the quality of my life right now	. 0	1	2	3	4
GS2	I get emotional support from my family	0	1	2	3	4
Sp21	I feel hopeful	. 0	1	2	3	4
GE1	I feel sad	. 0	1	2	3	4
Pal4	I feel like a burden to my family	. 0	1	2	3	4
Pal5	I am constipated	0	1	2	3	4
Pal14	I am able to openly discuss my concerns with the people closest to me	. 0	1	2	3	4
В1	I have been short of breath	. 0	1	2	3	4

A8 – PROMIS® Pain Interference Scale

In the past 7 days...

	Not at all	A little bit	Somewhat	Quite a bit	Very much
How often did you feel emotionally tense because of your pain?		2	3	4	5
How much did pain interfere with your close personal relationships?	1	2	3	4	5
How much did pain feel like a burden to you?	1	2	3	4	5
How irritable did you feel because of pain?	1	2	3	4	5
How often did pain make you feel discouraged?	1	2	3	4	5
How often did pain make you feel anxious?	1	2	3	4	5
How often did pain make you feel depressed?	1	2	3	4	5
How often was pain distressing to you?	1		3	4	5

A9 – Life Attitude Profile – revised, Death acceptance subscale

Life attitude profile revised (LAP-R) – Death Anxiety

	SA	\mathbf{A}	MA	U	N	MD		D)	S	D
5	Strongly	Agree	Moderately	ely Undecided Moderately		ely	Disag	gree	Stro	ngly	
	Agree		Agree		Dis	agre	ee			Disagre	
1.		ım generally n those arou	much less concer nd me.	ned about	SA	A	MA	U	MD	D	SD
2.	Death ma another.	kes little dif	ference to me one	way or	SA	A	MA	U	MD	D	SD
3.	Even thou about it.	agh death av	vaits me, I am not	concerned	SA	A	MA	U	MD	D	SD
4.	I would n	either fear d	eath nor welcome	it.	SA	A	MA	U	MD	D	SD
5.		th is a natur	al aspect of life, th	nere is no	SA	A	MA	U	MD	D	SD
6.	Some peo	ople are very	frightened of dea	th but I am	SA	A	MA	U	MD	D	SD

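### Five of the eight pain-interference items on form A8 ask 'How often', but the only answers printed are amounts

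*Combined protocol and SAP*

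**What the plan says.** Section 5.1.5 introduces the PIS as part of a standardized measurement initiative and says: "We will use 8 validated items pertaining to social and emotional consequences of pain during the previous week". Patients rate the items on a 5-point Likert scale, and the scale is collected only when the patient indicates pain at that assessment.

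Form A8 in Appendix A prints the eight items under one row of five answers, from 'Not at all' to 'Very much', with a recall period of the past 7 days. Some items ask about amount, such as "How much did pain interfere with your close personal relationships" and "How much did pain feel like a burden to you". Others ask about frequency, such as "How often did you feel emotionally tense because of your pain" and "How often did pain make you feel discouraged".

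Section 13.2.2 gives the scale a domain of its own: "Physical domain: PIS". Section 13.3.3 plans a repeated measures analysis of change from V1 for each secondary efficacy endpoint, with comparisons against baseline at the 0.05 level. Under Visit V1 in Section 5.1.2, baseline questionnaires are completed on paper, by the patient alone or with a staff member's help.

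**The concern.** A question that asks how often something happened needs an answer that expresses frequency. A8 offers none. A patient who meets a 'How often' item and sees 'Somewhat' or 'Quite a bit' must either translate a frequency into an amount or answer a different question, namely how strongly. The form does not say which.

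A patient with rare but intense distress from pain and a patient with constant mild distress could therefore tick the same box. The same patient could also read the item one way at V1, when alone with the paper form, and another way at V5 or V6, when helped. The change from V1 would then partly reflect a change of reading. With 15 patients planned, and the PIS collected only from those reporting pain, a few changed readings could matter to the summary.

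**Working it through.** **Inputs.** The item stems and answer row come from form A8. The planned number of items comes from Section 5.1.5, and the role of the scale from Sections 13.2.2 and 13.3.3.

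**Step 1: reproduce the plan's own figure.** Section 5.1.5 plans 8 items and A8 prints 8. The two agree.

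**Step 2: classify the stems.**

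| Item on A8 | Topic | Stem | Fits an amount answer? |
|---|---|---|---|
| 1 | emotionally tense | How often | No |
| 2 | close relationships | How much | Yes |
| 3 | burden | How much | Yes |
| 4 | irritable | How irritable | Yes |
| 5 | discouraged | How often | No |
| 6 | anxious | How often | No |
| 7 | depressed | How often | No |
| 8 | distressing | How often | No |

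Frequency stems: 5 of 8 = 62.5%. Amount or degree stems: 3 of 8 = 37.5%.

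**Step 3: share of the score, under an assumption.** The plan states no scoring rule for the PIS. If each item were scored 1 to 5 and the scores summed with equal weight:

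- the total would run from 8 × 1 = 8 to 8 × 5 = 40, a span of 32;
- the five frequency items would run from 5 × 1 = 5 to 5 × 5 = 25, a span of 20;
- their share of the span would be 20 / 32 = 62.5%.

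The share by item count is 62.5% whatever the scoring rule. The share of the score holds only under equal weights.

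**Step 4: compare with other forms in Appendix A.**

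- A10 (social isolation) prints frequency answers whose fourth option is 'Usually'.
- A18 (caregiver quality of life) prints two rows over the same boxes. One is a frequency row whose fourth option is 'Often'; the other is an amount row.
- A8 prints an amount row only.

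The appendix thus contains frequency answers elsewhere, but two different sets of them, and neither is tied to A8.

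**Step 5: size of the effect.** Nothing in the documents links a frequency reading to an intensity reading of these items, so no score shift can be calculated.

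**The case against.** There is a good deal to say on the other side.

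- **The page may have been read incompletely.** The table text of A8 has lost two answer digits in conversion (items 1 and 8), so a second answer row might also have been lost. This cannot be excluded without looking at the PDF page, but it is unlikely. All five labels of the A8 row survived, and so did the two rows of A18 and the frequency row of A10.
- **Other forms also mix wording.** The DS-II instruction asks how much or how strongly, above answers from 'Never' to 'Often', and the HADS uses 'Not at all' as the floor for some frequency answers. But DS-II items are statements, to which a frequency answer reads naturally. On A8 the question itself asks for a frequency.
- **The same form is used at V1, V5 and V6, so change within a patient keeps a constant format.** This stands for the format. It does not make the reading constant, because completion may be unaided at one visit and assisted at another.
- **The impact is small.** This stands. The PIS is one of many exploratory secondary outcomes in a single-arm pilot. FACIT-Pal 14 also asks about pain, nausea, energy, constipation and breathlessness, although Section 13.2.2 places it under global quality of life.

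A reader might go further and infer that PIS scores have lost comparability with data from the validated instrument. The documents do not support that: they cite the instrument's guide but do not reproduce its answer options. For the same reason they do not show that a particular set from 'Never' to 'Always' is the right replacement.

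**Conclusion.** The point holds as an ambiguity in the printed form. On five of eight items (62.5%), A8 asks for a frequency and offers only amounts, so the answers can be read in two ways. The scale concerned is the only one listed for the physical domain, and its change from V1 is analysed as a secondary efficacy endpoint. The feasibility and acceptability benchmarks in Section 13.1 are unaffected.

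The conclusion assumes that A8 as printed is what patients complete and that no second answer row stands on the original page. A reader might also infer that 25 of 40 raw points are compromised; that needs an equal-weight raw sum, which the plan does not state. Nor would correcting the answers stop the scale from combining frequency items with amount items. What the correction would achieve is that each item can be answered as asked.

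**What to change.** 1. Check A8, on the original page, and the corresponding data-entry form against the source instrument cited in Section 5.1.5.
2. For the five 'How often' items, print the frequency answer options given by that instrument. Take them from the source rather than borrowing those of A10 or A18, which differ from each other.
3. Keep the amount answers for the two 'How much' items and the 'How irritable' item.
4. If patients have already completed the printed form, keep the version constant within each patient, flag those scores, and summarise the two form versions separately.

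The cost is a one-page form correction, a matching change to data entry if it carries the same answers, and no added items or visits. The downside is that scores from the two versions are not directly comparable, so an already small set of PIS data may have to be shown in two parts.
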